**9.1.14 Signs and Symptoms Evaluation**

When a subject initiates a new IV, oral or inhaled antibiotic, the presence of specific signs and symptoms will be assessed and documented. These data will be used to determine the incidence of a protocol defined pulmonary exacerbation based on the definition in Appendix 2.

**9.1.15 Adverse Events**

Information regarding occurrence of AEs will be captured throughout each subject's study participation, starting after the first dose of study drug and ending once the subject has

terminated from the study. Duration (start and stop dates), grade, seriousness, outcome, treatment and relation to study participation will be recorded on the CRF.

## 9.2 Clinical Laboratory Measurements

### 9.2.1 Pregnancy Test

Urine or blood (approximately 2 cc) will be collected from females who are of childbearing potential for a pregnancy test as noted in the Schedule of Events and tested by the site according to site standard procedures.

### 9.2.2 Sputum Collection for Microbiological and Host Response Analysis

Expectorated sputum will be collected from subjects who are able to produce sputum as noted in the Schedule of Events. The samples collected will be stored frozen at -70 to -80°C at the site and batch shipped as instructed by the Therapeutics Development Network Coordinating Center (TDNCC). Instructions for specimen collection, processing, storage and shipping of samples will be provided in the Study Laboratory Manual. Processed aliquots will be banked for future analysis.

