### 5.2 Secondary Endpoints

#### Randomized Period

Secondary Endpoints:

- Difference between the azithromycin and placebo treatment groups in the relative change in FEV1(liters) during administration of TISP from Visit 2 to Visit 3.
- Difference between the azithromycin and placebo treatment groups in the change from Visit 1 to Visit 3 in the Cystic Fibrosis Respiratory Symptom Diary (CFRSD) - Chronic Respiratory Infection Symptom Score (CRISS®)
- Difference between the azithromycin and placebo treatment groups in the change from Visit 1 to Visit 3 in the scales derived from the CFQ-R

Exploratory Secondary Endpoints:

- Difference in adverse event rates and rates of abnormal QTc parameters from Visit 1 through Visit 3 between the azithromycin and placebo treatment groups
- Difference in the proportion of subjects hospitalized from Visit 1 through Visit 3 between the azithromycin and placebo treatment groups
- Difference in the proportion of subjects

prescribed acute oral, inhaled and IV antibiotics from Visit 1 through Visit 3 between the azithromycin and placebo treatment groups

- Difference in the proportion of subjects experiencing a protocol-defined pulmonary exacerbation requiring antibiotic therapy from Visit 1 through Visit 3 between the azithromycin and placebo treatment groups
- Difference between the azithromycin and placebo treatment groups in the absolute change from Visit 1 to Visit 3 and Visit 2 to Visit 3 in FEV1 (liters and % predicted), absolute and relative change in FVC (liters and % predicted), and absolute and relative change in FEF25-75%
- Difference between the azithromycin and placebo treatment groups in the change from Visit 1 to Visit 3 in weight
- Difference in the change from Visit 1 to Visit 3 in sputum *Pa* bacterial density between the azithromycin and placebo treatment groups

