### **10.2 Visit 2 - Day 0 (visit window -2/+4 days)**

1. Administer PRO questionnaires (CFRSD-CRISS and CFQ-R).
2. Review subject diary.
3. Perform pill count on returned study drug.
4. Record any AEs.
5. Record changes to concomitant medications. If a new IV, oral or inhaled antibiotic was prescribed, ensure that a Signs and Symptoms form was completed.
6. Perform an abbreviated physical examination.
7. Measure and record height and weight.
8. Obtain and record vital signs.
9. Perform and record spirometry.
10. If able to expectorate sputum, collect expectorated sputum.
11. Provide subject diary.
12. Review inhaled tobramycin schedule and remind subject to take TISP between Visits 2 and 3.
13. Instruct subject to bring study drug bottle, any remaining capsules, and diary to Visit 3.
14. Schedule subject for Visit 3. Visit 3 should coincide with completion of approximately 4 weeks use of inhaled tobramycin combined with study drug.

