## 15 STATISTICAL METHODS AND CONSIDERATIONS

A detailed statistical analysis plan will be written that will describe all analyses that will be generated for this study. All analyses will be performed using SAS® (SAS Institute, Inc., Cary, NC, USA) or R (R Foundation for Statistical Computing, Vienna, Austria).

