### 15.4 Analysis of Secondary Endpoints

#### Randomized Period

Descriptive analyses and graphical displays will be used to summarize all secondary endpoints. Endpoints will be compared between the azithromycin and placebo treatment groups from Visit 1 through Visit 3.

All reported SAEs and AEs will be coded using MedDRA and grouped by body system. The incidence of AEs (including emergent abnormal QTc parameters) between the azithromycin and placebo treatment groups will be tabulated by seriousness, severity, and relationship to study drug. Rates of (S)AEs by System Organ Class (SOC) will also be summarized. Poisson regression modeling will be used to derive rate ratios and corresponding 95% confidence and to compare groups using a two-sided 0.05 level test. Histograms showing the frequency of the number of (S)AEs in each treatment group will be included.

The proportion of subjects permanently or temporarily discontinuing study drug will also be tabulated by treatment group. Drug discontinuation events will be categorized as: (1) Permanently discontinued study drug, (2) Permanently discontinued study drug and withdrew from study, and (3) Temporarily discontinued study drug. Reason for permanent drug discontinuation will be summarized. Compliance measures will be computed separately for the TISP and azithromycin /placebo therapies.

Continuous secondary endpoints including changes in sputum bacterial density, weight, patient-reported quality of life (as measured by scales derived from the CFQ-R and CFRSD-CRIS), and pulmonary function (FEV1 % predicted, FVC, and FEF25%-75%) will be modeled similarly to the primary endpoint. Predicted values for spirometry measures at each visit will be calculated using the Global Lung Initiative reference equations. Least squares means and the treatment effect for the change for each secondary endpoint from Visit 1 to Visit 3 will be presented as well as corresponding 95% confidence intervals and p-values. The relative change in FEV1(liters) during administration of TISP from Visit 2 to Visit 3 will be analyzed in a similar manner.

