1.1 Study Rationale and Design

Patients with cystic fibrosis (CF) commonly acquire a chronic airway infection with *Pseudomonas aeruginosa* (*P.a.*). Both inhaled tobramycin and oral azithromycin have been proven beneficial in these patients and are currently used by the majority of eligible patients. Seventy five percent of US patients prescribed inhaled tobramycin are also prescribed chronic oral azithromycin. We believe that azithromycin is inhibiting the anti-*P.a.* effects and clinical benefits of inhaled tobramycin. This study will investigate whether azithromycin is associated with poorer clinical and microbiologic outcomes as compared to placebo during concurrent administration of inhaled tobramycin.

This is a prospective, randomized, placebo-controlled, double-blinded study of azithromycin in subjects with chronic *Pa* airway infection using inhaled tobramycin. Subjects who have received two (2) or more cycles of inhaled tobramycin within the 24 weeks prior to enrollment will be recruited into the study. Approximately 120 eligible subjects (allowing for 10 withdrawn) will be enrolled and randomized to either azithromycin or placebo at Visit 1 (Day -14), approximately 14 days prior to the start day of their next planned 28-day nebulized solution or dry powder tobramycin (TISP) cycle. Subjects will be randomized in a 1:1 fashion to azithromycin (500 mg three times per week) or matched placebo.

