Between Visit 1 (Day -14) and Visit 2 (Day 0), a two-week run-in period will be used to begin administration of either azithromycin or placebo. Among those randomized to azithromycin, the 2-week run-in period will be used to initiate azithromycin and standardize uptake prior to the start of the next TISP cycle. Among those randomized to placebo, the run-in period will be used as a standardized washout prior to the start of the next TISP cycle. Subjects will begin TISP at Visit 2 in addition to their continued dosing of randomized study drug treatment (azithromycin or placebo). Subjects will continue both TISP and study drug dosing for 28 days (up until Visit 3), which corresponds with the end of a clinically prescribed 4-week cycle of TISP. Subjects completing the study through Visit 3 (Day 28) will be offered participation and consent to an 8-week open-label extension period during which azithromycin will be provided. During the open-label period, subjects will be instructed to remain off of TISP for the first 4-week period, followed by a 4-week period of TISP. Total duration of subject participation will be up to 6 weeks for those enrolled in the randomized study and up to 98 days for subjects participating in the optional open-label extension. Subjects who meet all inclusion criteria and none of the exclusion criteria will be eligible for the study.

The primary objective of this study is to determine if azithromycin impairs the previously-recognized clinical benefits of inhaled tobramycin by comparing changes in pulmonary function as measured by FEV₁ between subjects randomized to azithromycin versus placebo.

The secondary objectives for the randomized period are to:

- Compare changes in patient-reported quality of life between subjects randomized to azithromycin versus placebo

The secondary exploratory objectives for the randomized period are to:

- Compare the safety profile between subjects randomized to azithromycin versus placebo
- Compare changes in additional spirometry measures, bacterial density, and weight between subjects randomized to azithromycin versus placebo
- Compare rates of pulmonary exacerbations, hospitalizations, and acute antibiotic usage between subjects randomized to azithromycin versus placebo

The objectives for those continuing in the open-label extension:

- Among those randomized to azithromycin and remaining on azithromycin, obtain additional data to determine the long term effect of azithromycin on clinical outcomes

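### Sputum Pa density, the only microbiological endpoint, has no stated scale and no baseline-density adjustment in Protocol 15.4, and no analysis in the SAP text

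*Protocol*

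**What the plan says.** SAP 1.1 gives the aim as finding out whether azithromycin leads to "poorer clinical and microbiologic outcomes as compared to placebo during concurrent administration of inhaled tobramycin". Protocol 5.2 turns the microbiological half into one endpoint, listed last among the exploratory secondary endpoints: the Visit 1 to Visit 3 change in sputum Pa "bacterial density between the azithromycin and placebo treatment groups". No other microbiological endpoint is listed.

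Protocol 15.4 gives the analysis. The sentence beginning "Continuous secondary endpoints including changes in sputum bacterial density" groups density with weight, the quality-of-life scales and spirometry, and has them all modelled like the primary endpoint. Protocol 15.3 defines that model as linear regression adjusted for randomization strata. Least squares means, the treatment effect, a 95% interval and a p-value are promised.

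Protocol 15 says the SAP will "describe all analyses that will be generated for this study". SAP 1.1 repeats the objective: "Compare changes in additional spirometry measures, bacterial density, and weight between subjects randomized to azithromycin versus placebo". The analysis sections then cover enrolment, baseline, adherence, adverse events, spirometry (A.5), exacerbations and antibiotics (A.6), weight (A.7) and quality of life (A.8). None covers density. Protocol 15.2 lists Pa density as a baseline characteristic, and SAP A.2 carries a near-identical list without it.

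On the samples, Protocol 9.2.2 limits collection to subjects who can produce sputum and adds: "Processed aliquots will be banked for future analysis". Visit 2 is included (Protocol 10.2: "If able to expectorate sputum, collect expectorated sputum").

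**The concern.** The study's rationale is that azithromycin blunts tobramycin's action against Pa, and density is the endpoint that measures this most directly. Borrowing the FEV1 model leaves several choices open.

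- **Scale.** The protocol's own in vitro account uses logs (2-3 log antagonism, 100-1000 fold). Neither document gives a unit or transformation for sputum density.
- **Baseline.** The FEV1 model adjusts for baseline lung function at least coarsely, because FEV1 % predicted is a stratification factor. Density is not a stratification factor, so the same model adjusts for nothing that directly measures baseline density.
- **Low values.** There is no rule for results below the detection limit.
- **Analysis set.** Only subjects who expectorate contribute, and the plan does not say who is analysed when one of the two samples is missing.

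At stake is the precision and credibility of the mechanistic result. Without a prespecified scale and covariate, the estimate may be noisier than the data allow, and readers cannot tell which choices were fixed in advance.

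**Working it through.** **Step 1. Which endpoints reach the SAP.**

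| Objective in SAP 1.1 | Protocol analysis | SAP analysis section |
|---|---|---|
| Additional spirometry | 15.4 | A.5 |
| Bacterial density | 15.4 | none in A.1-A.8 |
| Weight | 15.4 | A.7 |

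SAP 1.2 describes Appendix B as the open-label period and Appendix C as listings of protocol violations and SAE narratives. A randomized-period density analysis would not be expected in either.

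**Step 2. The plan's own power figures.** The documents give power only for FEV1. With n = 55 per arm and two-sided 0.05, power = Φ(Δ / (SD·√(2/n)) − 1.96). For Δ = 7.5 and SD = 13, 7.5 / (13 × 0.1907) = 3.03, and Φ(1.07) is about 86%; the exact t calculation gives 85% (stated: 85%). For 8.65 and SD 13 it gives 93% (stated: 93%). For 6.3 and SD 11 it gives 84.5% (stated: 85%). These reproduce.

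**Step 3. Density on the log10 scale, no baseline term.** The documents give no SD, effect or number of paired samples for density, so every input here is an assumption. With a true difference of 1 log10 (10-fold), noncentral t power is:

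| Paired samples, both arms | SD of change 1.0 | 1.5 | 2.0 | 2.5 |
|---|---|---|---|---|
| 110 (100%) | ~100% | 93% | 74% | 55% |
| 88 (80%) | ~100% | 87% | 64% | 46% |
| 66 (60%) | 98% | 76% | 52% | 36% |
| 44 (40%) | 90% | 58% | 37% | 25% |

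The share of subjects with paired sputum matters as much as the SD.

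**Step 4. Adding Visit 1 log10 density.** Let both visits have SD σ and correlation r.

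- Change without baseline: SD = σ√(2(1−r)).
- Change adjusted for baseline: residual SD = σ√(1−r²).
- Variance ratio, adjusted to unadjusted: (1−r²) / (2(1−r)) = (1+r)/2.

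Assume σ = 1.5, 42 per arm (about 76% of 55) and a 1 log10 difference. At r = 0.5 the unadjusted SD is 1.50, the SE is 1.50 × √(2/42) = 0.327, and 1/0.327 = 3.06. The adjusted SD is 1.30, the SE is 0.283, and 1/0.283 = 3.53.

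| r | SD, change only | SD, adjusted | Variance ratio | Power, change only | Power, adjusted |
|---|---|---|---|---|---|
| 0.3 | 1.77 | 1.43 | 0.65 | 72% | 89% |
| 0.5 | 1.50 | 1.30 | 0.75 | 86% | 94% |
| 0.7 | 1.16 | 1.07 | 0.85 | 97% | 99% |

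If the log10 change is instead independent of baseline, the covariate explains nothing. At SD of change 1.5, power is 86% with or without it. The cost is one degree of freedom. None of these figures deducts degrees of freedom for the strata.

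**Step 5. What the scale could do.** Assume Visit 1 mean 7 log10 with SD 1.5, change SD 1.5 and mean placebo change −1 log10. Across true differences of 0.5 to 1.5 log10 and 22 to 55 per arm, simulated power on untransformed CFU is about 0.5-6% for absolute change and 2-23% for percent change. With 55 per arm and 1 log10, the three scales give 93% (log10), 13% (percent change) and 3% (absolute change).

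**The case against.** Protocol 15.4 does prespecify a test: it names density and fixes the model, the visits compared and the outputs. A reader of the SAP alone might infer that density goes untested, or that any density analysis would be chosen after unblinding. The protocol does not support either inference. What is open is the scale, the covariate, the handling of low values and the analysis set.

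A reader might also infer from Step 5 that the test has almost no power. That requires untransformed CFU, which no passage calls for. Protocol 5.2 says change for density and reserves relative change for spirometry. SAP A.7 and A.8 apply the same strata-adjusted regression to plain changes in weight and symptom scores, so the natural reading of 15.4 is that it borrows the model and not the percent scale. The background reports killing in logs, and most analysts would use log10 unprompted.

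The banking sentence is weak evidence of anything. The section heading refers to microbiological analysis, and processing is left to a laboratory manual that is not part of these documents.

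Finally, the endpoint is exploratory and the trial was not sized for it. The SAP text stops in A.8, and Appendices B and C are not reproduced.

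All of this stands, and it limits the point to an incomplete specification. It does not explain why density alone of the three paired objectives lacks a SAP section, why it left the baseline table, or why its own Visit 1 value is not a covariate.

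**Conclusion.** The point holds as a specification gap with a free gain in precision available. The density analysis exists in Protocol 15.4 but lacks a scale, a baseline-density term, a below-detection rule and an analysis set, and the SAP text does not carry it. Under equal SDs at the two visits, baseline adjustment multiplies the variance by (1+r)/2, a 15% to 35% reduction for r between 0.7 and 0.3. In the assumed setting, that adds 17, 8 and 2 percentage points of power at r = 0.3, 0.5 and 0.7. If change is unrelated to baseline, the gain is nil, at the cost of one degree of freedom.

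Every density figure rests on assumed inputs, so none is an estimate of this trial's actual power. The absence from the SAP is established only for A.1 to A.8. Given the exploratory rank, this is a worthwhile correction and does not threaten the primary conclusion.

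**What to change.** In Protocol 15.4 and a matching new SAP section:

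- Analyse sputum Pa density as log10 CFU/g.
- Regress the Visit 1 to Visit 3 change on treatment, the randomization strata and Visit 1 log10 density. Report the difference in log10 units or as a fold-change, with a 95% interval.
- State how values below the detection limit are handled.
- Define the analysis set as subjects with sputum at both visits, and report the number per arm, since only expectorating subjects contribute.
- Restore Pa density to the SAP A.2 baseline table, as in Protocol 15.2.

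Optionally, add the Visit 2 to Visit 3 density change as a supportive analysis. It covers the tobramycin period and parallels what SAP A.5 already does for spirometry.

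The core change costs wording and one model, with no new visits or samples. The Visit 1 and Visit 3 assays are already implied by the endpoint. The optional analysis adds the cost of assaying Visit 2 aliquots.

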## 10 EVALUATIONS BY VISIT

### Randomized Period

#### 10.1 Visit 1 – Day -14

\*A respiratory culture may be obtained prior to randomization to confirm eligibility criteria #4. If a respiratory culture is needed, the remaining Visit 1 procedures should be completed after confirming positive *Pa* culture results.

1. Review the study with the subject (subject's legal representative) and obtain written informed consent and HIPAA authorization and assent, if appropriate.
2. Assign the subject a unique study number.
3. If there is not a recent respiratory culture available, obtain culture to confirm eligibility:
  - Review culture results.
  - If *Pa* positive and meets criteria #4, schedule subsequent visit to complete remaining Visit 1 procedures.
  - If *Pa* negative, record as Screen Fail.
4. Review and record previous use of azithromycin and inhaled tobramycin.
5. Record demographics and CFF Registry ID, if consent obtained.
6. Record medical history, including a history of CF diagnosis and date.
7. Record concomitant medications.
8. Administer PRO questionnaires (CFRSD-CRISS and CFQ-R).
9. Perform a complete physical examination.
10. Measure and record height and weight.
11. Obtain and record vital signs.

12. Perform and record spirometry.
13. Collect blood or urine for pregnancy test (if female of child-bearing potential).
14. Obtain resting ECG.
15. If able to expectorate sputum, collect expectorated sputum.
16. Confirm subject eligibility.
17. Randomize to study drug.
18. Dispense study drug.
19. Review study drug dose and schedule with subject.
20. Provide subject diary and instructions for completion.
21. Remind subject to NOT use inhaled tobramycin between this day and Visit 2.
22. Instruct subject to bring study drug bottle, any remaining capsules, and diary to Visit 2.
23. Schedule subject for Visit 2.

### **10.2 Visit 2 - Day 0 (visit window -2/+4 days)**

1. Administer PRO questionnaires (CFRSD-CRISS and CFQ-R).
2. Review subject diary.
3. Perform pill count on returned study drug.
4. Record any AEs.
5. Record changes to concomitant medications. If a new IV, oral or inhaled antibiotic was prescribed, ensure that a Signs and Symptoms form was completed.
6. Perform an abbreviated physical examination.
7. Measure and record height and weight.
8. Obtain and record vital signs.
9. Perform and record spirometry.
10. If able to expectorate sputum, collect expectorated sputum.
11. Provide subject diary.
12. Review inhaled tobramycin schedule and remind subject to take TISP between Visits 2 and 3.
13. Instruct subject to bring study drug bottle, any remaining capsules, and diary to Visit 3.
14. Schedule subject for Visit 3. Visit 3 should coincide with completion of approximately 4 weeks use of inhaled tobramycin combined with study drug.

### **End of Randomized Period and Start of Open-Label Period**

### **10.3 Visit 3 – Day 28 (visit window -2/+4 days), Week 4**

1. Administer PRO questionnaires (CFRSD-CRISS and CFQ-R).
2. Review subject diary.
3. Perform pill count on returned study drug.

4. Record TISP use.
5. Record any AEs.
6. Record changes to concomitant medications. If a new IV, oral or inhaled antibiotic was prescribed, ensure that a Signs and Symptoms form was completed.
7. Perform abbreviated physical examination.
8. Measure and record height and weight.
9. Obtain and record vital signs.
10. Perform and record spirometry.
11. Obtain resting ECG.
12. If able to expectorate sputum, collect expectorated sputum.

### Visit 3: Additional procedures for subjects enrolling in the open-label extension

13. Assess subject eligibility for open-label extension
14. Review the open-label extension period of the study with the subject (subject's legal representative) and obtain written informed consent and HIPAA authorization and assent, if appropriate.
15. Dispense open-label azithromycin.
16. Provide subject diary.
17. Remind subject to NOT use inhaled tobramycin between this day and Visit 4.
18. Instruct to bring the azithromycin bottle, any remaining tablets, and diary to Visit 4.
19. Schedule subject for Visit 4.

